8 SAFETY ANALYSES

Safety analyses will be presented using the safety population.

8.1 Adverse Events

Adverse events will be coded using MedDRA, Version 23.0 or higher. Each event will be mapped to a system organ class and preferred term. A treatment-emergent adverse event (TEAE) is defined as an AE that occurs during the treatment period after first dosing through 30 days post-last dose. An on-treatment TEAE is defined as a TEAE that occurs during a treatment period after first dosing through the last dose. An off-treatment TEAE is defined as a TEAE that occurs during the first 30 days after the last treatment dose. Each TEAE will be assigned to a single treatment period according to the date of onset. TEAEs that continue over multiple treatment periods will be counted only once in the period during which the event started.

Related TEAEs include all those classified by the investigator as possibly, probably, or definitely related to the study drug. Unrelated TEAEs are those events classified as unlikely or not related..

Multiple events will be counted only once per subject in each of the previously mentioned summaries by treatment and onset (on-treatment, off-treatment, and overall). In the presentation, system organ class and preferred term (within each system organ class) will be sorted in order of descending frequency (by overall percentage of unique TEAEs) and then in alphabetical order, if necessary to break ties.

An overall summary of TEAEs will be provided summarizing subjects with at least 1 of the following: TEAE, related TEAE, severe TEAE, serious TEAE, related serious TEAE, TEAE leading to study discontinuation, or related TEAE leading to study discontinuation as well as the number of events within each of the previously mentioned categories by associated treatment and by onset (on-treatment, off-treatment, and overall). Subjects with at least 1 TEAE and the number of events will also be summarized by severity (mild, moderate, severe) and relationship to the treatment (unrelated, unlikely, possible, probable, definitely), by onset (on-treatment, off-treatment, and overall) within the associated treatment.

In addition, summaries of unique TEAEs will be presented by system organ class, preferred term, and by onset (on-treatment, off-treatment, and overall) within the associated treatment and will include the number and percentage of subjects who experienced the unique event for all TEAEs and all related TEAEs and number of events.

All AEs captured in the database will be presented in by-subject data listings and identified as a non-TEAE, on-treatment TEAE, or off-treatment TEAE. However, only TEAEs will be summarized.

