### **9.1 Laboratory Measurements**

#### **9.1.1 Chemistry panel**

A fasting (at least 9 h, water only) chemistry panel will be measured at screening visit 2 (day -14), treatment 1 visits 4 and 6 (days 1 and 29) and treatment 2 visits 8 and 10 (days 1 and day 29).

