### **9.2.6 12-lead ECG**

A 12-lead ECG will be performed at screening visit 3 (day -7) and at the end of each treatment (treatment 1 visit 6, day 29 and treatment 2 visit 10, day 29).

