## MAT-002 SUBJECT INSTRUCTIONS

### REMINDERS for Visits 6 and 10

- Your visit is scheduled on \_\_\_\_/\_\_\_\_/\_\_\_\_ @ \_\_\_\_:\_\_\_\_ am
- No food or drinks, except water for **at least 9 hours** before your next clinic visit.
- Drink plenty of fluids, water only, the evening before all clinic visits. Do not take study product before coming to the clinic.
- Maintain your regular physical activity patterns and avoid any vigorous physical activity **for at least 24 hours before** your next clinic visit.
- Avoid alcohol consumption for **at least 24 hours** before your next clinic visit.
- If a smoker/vaper, abstain from smoking/vaping for at least 1 hour prior to your next clinic visit.
- Notify the site if you are prescribed any new medication or begin taking a new supplement.
- Avoid all fish and seafood, other than 1 time per week.
- Avoid any fish or seafood for 48 hours before your next visit
- Avoid all vitamins/supplements/foods containing EPA/DHA (omega-3's).
- Continue to follow the TLC diet instructions.
- Please call the clinic at [**clinic phone number**] if you get sick and/or are prescribed an antibiotic.
- Record any questions or changes to your health/medications in the spaces provided below.

Comments:

---

---

---

---

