5 ANALYSIS POPULATIONS AND DATASETS

5.1 Definition of Analysis Populations

Statistical analysis and data tabulation will be performed using the following subject populations unless specified otherwise:

- Intention-to-treat (ITT) population;
- Safety population;
- Pharmacodynamic (PD) population;
- Per protocol (PP) population.

The ITT population will include all subjects who are randomized to a treatment sequence.

The safety population will include subjects who are randomized and receive at least one dose of any study treatment. This will be the primary population for safety analyses.

The PD population will include subjects for whom the estimation of PD parameters will be possible for 2 periods. This will be the primary population for PD analyses. PD parameters cannot be estimated accurately for subjects who have been off of study drug for an extended period prior to measurements. The half-life of EPA from Vascepa is approximately 89 hours (Vascepa Prescribing Information, accessed 01Dec20) and that for EPA from MAT9001 administered in the fed state is approximately 27 hours (MAT-001 clinical study report, 07Jul20). Measurements will not be used for PD estimation from samples obtained from subjects who have been off of study drug for 3 days (72 hours) or more.

The PP population will include all subjects who are included in the PD population for whom compliance for both study periods was at least 80%, and for whom no clinically important protocol violations or deviations occurred during the trial. All decisions regarding inclusion in the PP dataset will be made and documented prior to database lock.

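### SAP 8.1 ends the on-treatment window at the last dose, so an AE dated to the end-of-period laboratory tests or ECG is tabulated as off-treatment

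*SAP*

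**What the plan says.** **Classification (SAP 8.1).** "An on-treatment TEAE is defined as a TEAE that occurs during a treatment period after first dosing through the last dose". The next category starts where that one stops: "An off-treatment TEAE is defined as a TEAE that occurs during the first 30 days after the last treatment dose". The sort key is onset: "Each TEAE will be assigned to a single treatment period according to the date of onset". The overall summary is reported "by associated treatment and by onset (on-treatment, off-treatment, and overall"; the severity, relationship and system organ class/preferred term summaries use the same split, and the by-subject listings carry the label.

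**Dosing around the end-of-period visits.** Protocol section 5 has subjects arrive at visit 6 after a 9-15 h fast, and visit 10 follows the same procedures. The Appendix 6 reminder sheet for these visits says: "Do not take study product before coming to the clinic". Unused product is collected there, and Protocol 8.2 and 9.2.8 dispense only at visits 4, 5, 8 and 9.

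**Safety tests.** After screening, chemistry is drawn at "treatment 1 visits 4 and 6 (days 1 and 29) and treatment 2 visits 8 and 10 (days 1 and day 29" (Protocol 9.1.1). Hematology follows the same visits (9.1.2). Urinalysis is at visits 2, 6 and 10 (9.1.4). The ECG is done at screening visit 3 and "at the end of each treatment (treatment 1 visit 6, day 29 and treatment 2 visit 10, day 29" (9.2.6).

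**How the same visits are treated elsewhere.** The SAP Definitions place visits 6 and 10 inside Periods 1 and 2. Protocol 10.2 names day 29 as the on-treatment value for plasma omega-3. SAP 5.1 rejects samples only after a longer gap, of 72 hours or more: "Measurements will not be used for PD estimation from samples obtained from subjects who have been off of study drug for 3 days (72 hours)".

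**The concern.** The last dose of a period comes before visit 6 or 10, and every scheduled in-period safety laboratory test and ECG happens at that visit. An AE whose onset is dated to such a test falls after the on-treatment window has closed, although the subject stopped dosing only hours before. It is then counted with events that start up to 30 days into washout.

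At stake is the meaning of the on/off split, which the SAP carries through every TEAE table. A low on-treatment count of laboratory- or ECG-detected events would be partly produced by the definition, and the off-treatment column would mix findings in exposed subjects with findings well into washout. ECG results are otherwise only listed (SAP 9.3), so the TEAE tables are the only planned summary in which an ECG finding can be counted.

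**Working it through.** **1. Last planned dose.** SAP 9.2 gives 112 planned capsules for a 28-day period at 4 capsules a day: 28 × 4 = 112, which reproduces. With a day-29 visit, the last planned dose is therefore on day 28. The visit window is minus 2 days only (Protocol section 5). Because no product is taken before the visit, last planned dose day = visit day − 1:

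- visit on day 27: last dose on day 26
- visit on day 28: last dose on day 27
- visit on day 29: last dose on day 28

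**2. Tests against the dosing window.** Schedule from the Protocol section 6 flow chart and sections 9.1-9.2. Visits 4 and 8 are the baselines, listed before that day's dose in Protocol 9.3.

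| Test | Scheduled visits | In period, after first dose | Of these, at visit 5 or 9 (still dosing) |
|---|---|---|---|
| Chemistry | 2, 4, 6, 8, 10 | 6, 10 | none |
| Hematology | 2, 4, 6, 8, 10 | 6, 10 | none |
| Urinalysis | 2, 6, 10 | 6, 10 | none |
| ECG | 3, 6, 10 | 6, 10 | none |

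Four tests × two visits = 8 scheduled in-period test points, and all 8 follow the last planned dose.

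**3. One visit, two classifications.** Take a day-29 visit with the last dose on day 28.

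- AE dated to the day-29 sample or ECG: day 29 is later than day 28, so it is off-treatment. That category runs to day 28 + 30 = day 58.
- Pharmacodynamic sample from the same visit: about 9-15 h since the last dose, under 72 h, so it is used.

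**4. How exposed the subject is.** SAP 5.1 gives EPA half-lives of about 89 h (Vascepa) and 27 h (MAT9001, fed). Assume the last dose was taken with the last meal before the fast, and simple exponential decay. Fraction remaining = 2^(−t / half-life):

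| Time since last dose | 89 h half-life | 27 h half-life |
|---|---|---|
| 9 h | 0.932 | 0.794 |
| 15 h | 0.890 | 0.680 |
| 72 h | 0.571 | 0.157 |

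At the visit, about 89-93% (Vascepa) or 68-79% (MAT9001) of end-of-dosing EPA is still present.

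**The case against.** Four points can be made for the SAP.

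**Onset is not detection.** A reader might infer that every laboratory or ECG finding must be off-treatment. The documents do not support that. SAP 8.1 sorts by onset, and neither document says how to date an event found only by a test. An abnormality that goes with symptoms starting before the last dose could be given the earlier date and counted as on-treatment. This stands, and it limits the point to AEs dated to the scheduled test. The missing rule is itself a gap.

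**Not every abnormality is an AE.** Protocol 12.3 includes abnormal test results in its definition but then lists what makes an event count, such as needing treatment, further work-up beyond a confirmatory repeat, or clinically significant signs. This stands. The number of affected events may be small, and no count can be given.

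**Nothing is lost.** A reader might also infer that such events disappear, are charged to the wrong product, or distort the comparison of the two products. None of these follows. They remain TEAEs, are tabulated under the associated treatment and appear in the overall column. Chemistry, hematology and urinalysis results are summarized by treatment with no on/off split (SAP 8.2), and the rule is the same for both products. This stands in full.

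**72 hours is a rule for pharmacodynamic samples.** It was not written for AEs, and 57% of EPA from Vascepa would remain at 72 h on the calculation above. SAP 5.1 and 9.4 also word the limit differently (72 hours or more; more than three days), and AEs are assigned by date. This stands against an hours-based cut-off. It does not justify closing the window before the visit at which the scheduled safety tests are done.

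**Conclusion.** The point holds in a limited form. As written, SAP 8.1 labels as off-treatment any AE dated to a scheduled visit 6 or 10 laboratory test or ECG, in both periods and for both products. That covers all 8 of the scheduled in-period test points. It conflicts with the protocol's use of day 29 as on-treatment for plasma omega-3 and with the SAP's acceptance of samples from the same visit.

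The damage is confined to the on/off split in the TEAE tables and to the labels in the listings. Overall TEAE counts, attribution to product, laboratory summaries and all efficacy analyses are unaffected. It is worth correcting because the SAP reports this split throughout and the correction is cheap.

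The conclusion assumes that subjects follow the instruction not to dose before the visit and that a test-only finding is dated to the test. The exposure figures also assume a last dose 9-15 h before the visit and simple decay; the classification result does not depend on them. Early-termination or unscheduled tests done while a subject is still dosing are outside this point.

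**What to change.** Amend SAP 8.1 in calendar dates:

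- **On-treatment:** onset from the first dose of a period through the date of that period's end-of-treatment visit (visit 6 or 10), provided that date is within 3 days of the last dose; otherwise through the last dose date plus 3 days.
- **Off-treatment:** onset from the day after that window closes to 30 days after the last dose.
- **Dating rule:** an AE detected only by a test takes the date of the sample or ECG as its onset.

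Dates avoid any need for AE onset times and suit the by-date assignment already in SAP 8.1.

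The cost is a few sentences in the SAP and a small change to the derivation of the on/off flag. No visit, dosing or data-collection procedure changes. The one downside is that the few symptoms starting between the last dose and the end of the new window also move to the on-treatment column.

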### Footnotes:

To adjust for subject scheduling, the allowable window to complete all screening procedures will not exceed 42 days with a minimum of 48 hours between all visits. If the subject is already following a Therapeutic Lifestyle Changes (TLC) diet at visit 1 supported by the MEDFICTS score, they can proceed directly to visit 2 procedures. A TLC diet lead-in of 14 days prior to the qualification visit (visit 2, day -14) will be required. A window of  $\pm 2$  days will be allowed for visits on day 22 (visits 5 and 9); the window for visits on day 29 (visit 6 and 10) is will be minus 2 days only, i.e., days 27, 28 or 29. The washout period between treatments (between visits 6 and 7) should be a total of at least 28 days, but not more than 35 days.

HIPAA = Health Insurance Portability and Accountability Act authorization for disclosure of protected health information. Signed document authorizes the use and disclosure of the subject's Protected Health Information by

the Investigator and by those persons who need that information for the purposes of the study. If a subject does not require a dietary lead-in based on MEDFICTS score, the first two visits should be combined.

Study procedures include assessments of height (visit 1 only), weight, vital signs (heart rate and blood pressure), waist circumference, evaluation of inclusion and exclusion criteria (visits 1 - 4), review of continuation requirements (visits 5 - 10) and concomitant medication use.

Medical history will be completed with visit 1 procedures.

Glycated hemoglobin (HbA1c) will be analyzed only for subjects with a history of type 2 diabetes mellitus OR a fasting glucose concentration  $\geq 126$  mg/dL.

Thyroid stimulating hormone (TSH) will be assessed at screening visit 2 (day -14). Uncontrolled hyper- or hypothyroid conditions are exclusionary based on the opinion of the Investigator.

Plasma and/or serum and/or blood cells will be collected, processed and stored for possible later analysis of non-genetic analytes for assessment of cardiometabolic health and/or lipid metabolism.

A urine pregnancy test will be performed for all women  $< 60$  y of age.

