Subjects will receive instruction on the Therapeutic Lifestyle Changes (TLC) diet at the first screening visit and instructions will be reinforced for the duration of the study. Subjects will continue to follow the TLC diet during the washout between treatment periods.

The Meats, Eggs, Dairy, Fried Foods, In baked goods, Convenience foods, Table fats, Snacks (MEDFICTS) Dietary Assessment Questionnaire will be completed at screening to determine whether the subject is already following a TLC diet, and it will be completed periodically during the study to evaluate compliance with the TLC diet instructions. If the subject is not following a TLC diet at screening, a TLC diet lead-in of 28 days prior to the first treatment phase (visit 4, day 1) will be required.

At the conclusion of visit 6, subjects will begin a washout period of at least 28 days, but not more than 35 days, prior to visit 7.

The first dose of the study product for that treatment period will be administered at the clinic with a TLC-compliant meal replacement bar.

Fasting plasma and plasma phospholipid levels of EPA, DHA, DPA and total omega-3 fatty acids will be assessed. Fatty acids from RBCs will be analyzed from samples collected at visit 4, 5 and 6 only (treatment 1).

Fasting levels of TG, total-C and HDL-C will be measured, non-HDL-C, LDL-C, VLDL-C will be calculated. A minimum of 50% of enrolled subjects will have a TG value  $\geq 200$ -499 mg/dL as assessed at screening.

Fasting levels of Apo A1, Apo B and Apo C3 will be measured.

Treatment emergent AE's will be assessed at visits 4 through 10. AEs that occur prior to visit 4 will be considered medical history. AEs will also be collected from spontaneous subject reporting at any time during the study.

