## 12.3 Adverse Event Monitoring

An AE is defined as any untoward medical occurrence in a clinical investigation subject following written informed consent that does not necessarily have a causal relationship with the study product. An AE can be any unfavorable or unintended sign (including an abnormal finding), symptom, or disease temporally associated with the use of an investigational product whether or not related to the investigational product.

This includes any occurrence that is new in onset or aggravated in severity or frequency from the baseline condition, or abnormal results of diagnostic procedures (including laboratory test abnormalities).

Events should be considered AEs if they:

- Result in discontinuation from the study;
- Require treatment or any other therapeutic intervention;
- Require further diagnostic evaluation (excluding a repetition of the same procedure to confirm the abnormality);

- Are associated with clinical signs or symptoms judged by the Investigator to have a significant clinical impact.

Events that occur with comparable frequency and severity to the subject's baseline condition should not be considered AEs. Elective hospitalizations planned prior to a subject providing informed consent (e.g., elective cosmetic procedures) are not AEs. If a woman becomes pregnant during the study, the subject must be immediately discontinued from study product, and the pregnancy followed through to delivery. Every effort will be documented to retrieve the information on both mother and child at the time of delivery.

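### SAP 8.1 attributes adverse events by onset date with no rule for worsening, so an event that worsens on the second product can be tabulated under the first

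*SAP*

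**What the plan says.** SAP 8.1 gives the attribution rule in two sentences: "Each TEAE will be assigned to a single treatment period according to the date of onset", and "TEAEs that continue over multiple treatment periods will be counted only once in the period during which the event started". Treatment emergence is defined by timing alone: "A treatment-emergent adverse event (TEAE) is defined as an AE that occurs during the treatment period after first dosing through 30 days post-last dose". The off-treatment subset is bounded in the same way: "An off-treatment TEAE is defined as a TEAE that occurs during the first 30 days after the last treatment dose". Everything else is listed by subject with a status flag, but "However, only TEAEs will be summarized". The summaries of severe, serious, related and discontinuation events are all broken down by product, so they inherit the onset rule.

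Protocol 12.3 defines an adverse event more broadly: "This includes any occurrence that is new in onset or aggravated in severity or frequency from the baseline condition". Protocol 11.7 bases the safety assessment mainly on how frequent and how severe adverse events are, tabulated by treatment. Protocol 12.3.5 says that adverse events go on the eCRF page. It does not say whether worsening of an ongoing event opens a new record. Where the two documents differ on analysis, the SAP governs (Protocol 11, SAP 4).

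On timing, Protocol 6, footnote 1 says "The washout period between treatments (between visits 6 and 7) should be a total of at least 28 days, but not more than 35 days", and footnote 11 agrees: "subjects will begin a washout period of at least 28 days, but not more than 35 days, prior to visit 7". Protocol 5 puts visit 7 seven days before the next treatment period. In its account of visit 6, however, the same section can be read as giving 28 to 35 days for the whole interval up to crossover.

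**The concern.** In a two-period crossover, a subject can carry an ongoing event from one product into the other. The period of onset is then not always the period in which the event became important. An onset-only rule with no provision for worsening can credit the later severity, seriousness or discontinuation to the product the subject was no longer taking.

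The SAP re-baselines other safety data at each period: laboratory values in 8.2, vital signs and body weight in 8.3. Adverse events get no equivalent treatment.

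What is at stake is the descriptive comparison of the two products on severe, serious and discontinuation events. Misattribution moves a worsening from the Period 2 product to the other column. In a narrower case it leaves the event out of the tables altogether.

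**Working it through.** The documents give no event rates, and there is no planned figure to reproduce. The check has two parts: following the rule through the possible cases, and calendar arithmetic on the washout.

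**Part 1. An event that starts on the first product and worsens on the second**

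- *One record kept open.* The onset date lies in Period 1, or in the 30 days after its last dose. The event is assigned to the first product and counted once. If the record carries the later grade, seriousness or action taken, those attributes are tabulated under the first product.
- *New record opened at worsening.* The new record has a Period 2 onset date, and the same SAP rule assigns it to the second product.

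Neither document says which of these a site should do. Protocol 12.3 might permit the second, because it counts aggravation as an adverse event. However, it measures aggravation from a baseline condition and does not say which period's baseline applies. Attribution therefore depends on recording practice. This part does not depend on the length of the washout.

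**Part 2. An event that starts late in washout and worsens on the second product**

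Inputs:
- *a*, last Period 1 dose to visit 6: 0 or 1 day. This is an assumption. Protocol Appendix 6 tells subjects not to take product before coming to visit 6, which favors 1 day.
- *b*, washout: 28 to 35 days (Protocol 6, footnotes 1 and 11).
- *c*, visit 7 to visit 8: day -7 to day 1 with no day 0, which is 7 days.
- Window: 30 days after the last dose (SAP 8.1), read as the last dose of each period.

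Formula when washout ends at visit 7: uncovered days = a + b + c − 30. When 28 to 35 days is the whole interval to crossover, c drops out: uncovered days = a + b − 30, with a floor of 0.

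| Reading of washout | a | Off-drug gap (days) | Uncovered days |
|---|---|---|---|
| Visit 6 to visit 7 | 0 | 28+7 to 35+7 = 35 to 42 | 5 to 12 |
| Visit 6 to visit 7 | 1 | 36 to 43 | 6 to 13 |
| Total before crossover | 0 | 28 to 35 | 0 to 5 |
| Total before crossover | 1 | 29 to 36 | 0 to 6 |

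The ranges are therefore 5 to 13 days on the first reading and 0 to 6 on the second. They count up to the day of crossover; full days strictly before it are one fewer wherever the count is above zero. An event that starts in that interval is not treatment-emergent. If it worsens in Period 2 under the same record, it appears only in the listings.

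If the last dose is instead read as the last of the whole study, late-washout events are treatment-emergent. Their product is still unstated, because the SAP definitions limit Period 1 to visits 4 to 6 and Period 2 to visits 8 to 10.

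**The case against.** The strongest reply is that the documents do not establish misattribution. It needs a single record that keeps its original onset date, and the eCRF completion instructions that might settle this are not among the documents. That stands. A reader might infer that the SAP always charges a Period 2 worsening to the first product. The text supports this only where one record is kept.

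A reader might also infer that late-washout events certainly belong to neither product. That is not settled. Protocol 9.2.10 assesses treatment-emergent events at visits 4 to 10, which include washout visit 7, and sends only events before visit 4 to medical history. This fits a study-wide window. The SAP's 30-day off-treatment definition fits a per-period window better, but the text is open. The two wordings of the washout also allow the uncovered interval to be zero.

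It would be tempting to size the problem by multiplying uncovered days by the 85 evaluable subjects. That would measure time outside a window, not misassigned events. An affected event must start in those days, persist, worsen in Period 2 and receive no new record, and the documents give no rate for any of these steps. In addition, 85 is the efficacy sample, whereas the adverse event tables use the safety population.

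The consequences are limited. SAP 8.1 plans no hypothesis test on adverse events. Every event is listed by subject, and serious events are reported within 24 hours and followed individually (Protocol 12.3.4 and 12.3.6). Counting a continuing event once is also a recognizable way to avoid double counting. None of this supplies the missing rule: the by-product tables still depend on how sites happen to record a worsening.

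**Conclusion.** The concern holds in a limited form. SAP 8.1 is explicit that onset date decides attribution, and it makes no provision for worsening. Followed as written with one record per event, it places a Period 2 worsening, a change to serious, or a discontinuation under the Period 1 product. This conclusion assumes only that at least some sites keep one record open, which neither document prevents.

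The late-washout gap is secondary and conditional. It is about 5 to 13 days per on-schedule subject if the window is per period and washout ends at visit 7. It is 0 to 6 days if 28 to 35 days is the whole interval to crossover. Under a study-wide window the events are summarized but have no stated product.

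The number of affected events is unknown, so no claim can be made that the safety comparison would change. The efficacy analyses, the listings and serious-event reporting are untouched. This is worth correcting because the correction is cheap.

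**What to change.** Add to SAP 8.1:

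- An adverse event already ongoing at a period's first dose, including one with onset in washout, whose severity grade increases or which becomes serious after that dose is counted as a treatment-emergent event of that period's treatment at the higher grade. The earlier treatment, if the event was already counted there, keeps the grade held before the change.
- The 30-day window runs from the last dose of each period.

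Add an eCRF completion note asking sites to enter the worsening as a separate adverse event record with its own date, so that the tables can be produced without judging events case by case.

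This wording is triggered by grade and seriousness. The SAP should also say whether a rise in frequency alone, or a discontinuation at unchanged grade, is to be re-attributed or left with the earlier treatment. The two descriptions of washout length in the protocol should be reconciled, although the worsening rule works under either.

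The cost is a short SAP edit and a site instruction. The small downside is that one underlying event can appear under both products; a table footnote can say so.
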